11.1. PK Sampling Schedule

The PK sampling schedule of MP1032 in plasma on Day 1, and Day 7 is mentioned in Table 1 Section 4.6. In summary, PK samples will be collected via sparse sampling from a PK subset of approximately 30 patients (who give optional consent) in a 2:1 ratio (approximately 20 patients from the 300 mg MP1032 BID plus SoC group and approximately 10 patients from the placebo group plus SoC group) to assess the PK of MP1032 on Day 1 (single dose) and Day 7 (steady state). A total of 16 samples (approximately 4.9 mL per time point for a total of approximately 78.4 mL) will be collected relative to the first dose on Day 1 and the first dose on Day 7. Samples on Day 1 and Day 7 will be collected predose (within 10 minutes before the first daily dose) and postdose at 10 minutes, 20 minutes, 30 minutes, 60 minutes, 120 minutes, 8 hours (before next dose), and 24 hours before the next morning dose (if applicable), if possible. Patients who provide consent for the PK sampling, but are no longer hospitalized on Day 7, will not have Day 7 PK samples collected.

11.2. Plasma PK Endpoint

The following PK parameters will be calculated by standard non-compartmental methods with MP1032 plasma concentrations, using up to 8 hours post-dose, on Day 1 and Day 7 for fasting condition (or fed, if fasting not possible):

AUC0-inf:	Area under the concentration-time curve from time zero to infinity (extrapolated), calculated as AUC_{D-t} + Ct/K_{el} , where Ct is the last observed non-zero concentration.
AUC0-t:	Area under the concentration-time curve from time zero to the last non-zero concentration. The calculation of AUC _{D-t} will be done using the linear trapezoidal method using linear trapezoidal linear interpolation.
C _{max:}	Maximum observed concentration.
Clast:	Last observed concentration.
t _{max} :	Time of observed C _{max} .
T _{%el} :	Elimination half-life, calculated as In (2)/Kel.
Residual area:	Residual area, calculated as 100*(1- AUCo+/ AUCo+mr).
	If Residual Area is >20%, then AUC _{D-Inf} is considered unreliable; due to which all related PK parameters of AUC _{D-Inf} (CI/F, Vz/F, Residual area, and AUC _{D-Inf}) will be flagged in individual listings, and excluded from summary statistics if residual Area is >20%.
Kel:	Elimination rate constant. This parameter will be the negative of the estimated slope of the linear regression of the In-transformed plasma concentration versus time

This document is confidential.

SAP Text Version: 2.0, 31-Aug-2022 Controlled Document ID: CC , Effective Date 31-Aug-2020 Filing requirements: TMF

Page 39 of 56

profile in the terminal elimination phase. Best fit method will be used to calculate the K_{el} from at least 3 post C_{max} concentration data points excluding the C_{max}. The timepoint where In-linear K_{el} calculation begins (K_{el Lower}) and the actual sampling time of the last measurable concentration used to estimate the K_{el} (K_{el Upper}), as well as the R_{sq} adjusted for the In-linear regression for the calculation of the elimination rate constant will be reported. R_{sq} adjusted, the goodness of fit statistic for the terminal elimination phase, adjusted for the number of points used in the estimation of K_{el} must be ≥ 0.8 . If the K_{el} cannot be measured (eg: fewer than 3 non-zero concentrations in the terminal elimination phase), then K_{el}, and its related PK parameters (K_{el}, K_{el Lower}, K_{el Upper}, AUC_{D-Inf}, Residual area, T₃₂el, CI/F, and V₂/F) will not be reported for PK profiles. If the R_{sq} adjusted is <0.8, then K_{el}, and its related PK parameters (K_{el}, K_{el Lower}, K_{el Upper}, AUC_{D-Inf}, Residual area, T₃₂el, CI/F, and V₂/F) will be will be included and flagged in the listings but will not be included in the summary statistics.

CI/F Apparent total body clearance (CI/F), estimated as Dose/AUC_{0-Inf} (Day 1 only).

V₂/F Apparent volume of distribution (V₂/F), estimated as Dose/(K_{el} x AUC_{D-Inf}) (Day 1 only).

For Day 2 (or 24 hours after Day 1), Day 7, and Day 8 (or 24 hours after Day 7):

Ctrough: Pre-dose concentration (Day 2, 7, and 8).

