5.5. Pharmacokinetic Endpoints

 MP1032 plasma concentrations and PK parameters (if possible) including maximum observed plasma concentration, area under the concentration-time curve, elimination parameters, apparent body clearance, apparent volume of distribution, trough concentration, average observed plasma concentration at steady state, and other relevant PK parameters assessed via MP1032 plasma exposure on Day 1 and Day 7 in a PK subset of patients.

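### Average steady-state concentration is listed as a PK endpoint but never derived, and the Day 7 AUCs (to infinity, or to at most 8 h) do not measure dosing-interval exposure

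*SAP*

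**What the plan says.** - **Endpoint list (SAP 5.5).** The list opens with "MP1032 plasma concentrations and PK parameters (if possible") and includes "trough concentration, average observed plasma concentration at steady state, and other relevant PK parameters".
- **Derivation (SAP 11.2).** Parameters are calculated "using up to 8 hours post-dose, on Day 1 and Day 7 for fasting condition". They include AUC0-inf, defined as "Area under the concentration-time curve from time zero to infinity (extrapolated"), and AUC0-t, defined as "Area under the concentration-time curve from time zero to the last non-zero concentration". Clearance is "estimated as Dose/AUC_{0-Inf} (Day 1 only") and Vz/F is limited in the same way. AUC0-inf and residual area carry no such limit. Ctrough is added for Days 2, 7 and 8. AUC0-inf is flagged in listings and "excluded from summary statistics if residual Area is >20"%.
- **Summary (SAP 11.4.1).** The table covers AUCs, Cmax, Ctrough, CL/F, Vz/F, half-life, Kel and tmax. It has no row for average concentration.
- **Design (SAP 4.5 and 11.1).** Dosing is twice daily, roughly 12 hours apart and never less than 8. Day 7 is described as steady state. After the 120-minute sample only 8 h and 24 h samples follow, and the 8 h sample is labelled as preceding the next dose.

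**The concern.** SAP 11.2 is where this plan defines its PK parameters, so an endpoint named in 5.5 should either have a formula there or be declared not derivable. Average steady-state concentration has neither, and section 16 records no change.

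It cannot be recovered from the parameters that are defined. It equals AUC over the dosing interval divided by the interval, and that AUC is not among them. On Day 7 the plan instead reports one area that runs past the interval and counts drug carried over from earlier doses, and one that stops at 8 h. The plan already treats CL/F and Vz/F, which are built on AUC0-inf, as Day 1 quantities, but it leaves AUC0-inf itself on both days.

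At stake are a listed PK endpoint and a correct description of steady-state exposure in the PK subset.

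**Working it through.** **The plan's own figure.** 11.1 gives 16 samples and 78.4 mL. Predose, 10, 20, 30, 60 and 120 min, 8 h and 24 h make 8 times; 8 × 2 days = 16, and 16 × 4.9 mL = 78.4 mL. This agrees. Seven of the eight times on each day lie within the 8 h used for derivation.

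**Inputs.** tau = 12 h, taken from 4.5 for the arithmetic only. Last profile sample at 8 h and residual-area limit of 20%, from 11.1 and 11.2. The half-life h is not given, so it is varied; k = ln 2 / h.

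**Formulas.** At steady state with a log-linear tail, AUC0-inf = AUCtau + C(tau)/k. For mono-exponential decline:

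- AUC0-inf / AUC0-12 = 1 / (1 − e^(−12k))
- residual area at 8 h = e^(−8k)
- AUC0-8 / AUC0-12 = (1 − e^(−8k)) / (1 − e^(−12k))

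Example at h = 3 h: e^(−12k) = 2^(−4) = 0.0625, so the first ratio is 1/0.9375 = 1.067.

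| h (hours) | AUC0-inf / AUC0-12 | Residual at 8 h | AUC0-8 / AUC0-12 |
|---|---|---|---|
| 1 | 1.000 | 0.4% | 0.996 |
| 2 | 1.016 | 6.25% | 0.952 |
| 3 | 1.067 | 15.7% | 0.899 |
| 3.445 | 1.098 | 20.0% | 0.879 |
| 4 | 1.143 | 25.0% | 0.857 |

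The 20% limit is reached at h = 8 ln 2 / ln 5 = 3.445 h. Cases beyond it, such as 4 h, leave the summaries but stay flagged in the listings. A one-compartment oral model (assumed absorption rates 1.5 to 6 per hour) gives an AUC0-inf ratio of 1.069 to 1.079 at h = 3 h, so the result does not hinge on the mono-exponential shape.

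**Effect of the sampling gap.** 11.2 uses the linear trapezoid, which overstates a convex decline between 2 h and 8 h. Applying it to the scheduled times, each result divided by the true AUC0-12:

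| h (hours) | AUC0-inf as in 11.2 | AUC0-12 with 8–12 h from Kel | AUC0-8 |
|---|---|---|---|
| 2 | 1.17 | 1.15 | 1.10 |
| 3 | 1.15 | 1.08 | 0.98 |
| 3.445 | 1.16 | 1.06 | 0.94 |

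The trapezoid error is the same absolute amount in all three columns. The interval AUC is closer to the truth than AUC0-inf in every row. The apparent accuracy of AUC0-8 at 3 h comes from two errors offsetting each other.

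**If tau were 8 h.** By definition AUC0-inf / AUC0-8 = 1 / (1 − residual), so the 20% rule would cap the excess at 1/0.8 = 1.25, that is 25% rather than about 10%. The answer depends on which interval is meant, so tau has to be stated.

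**The case against.** **The endpoint is conditional.** 5.5 says parameters are reported where possible, and the sampling is sparse. This stands as a reason not to call the average concentration a firm promise. It does not close the gap, because 11.2 neither gives a method nor says that it cannot be derived.

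**AUC0-inf is labelled for what it is, and little depends on it on Day 7.** This largely stands. A reader might infer that the plan will report false accumulation by comparing Day 7 with Day 1 AUC0-inf. The SAP does not support that: no accumulation ratio or Day 7/Day 1 comparison is planned, and PK parameters are only listed and described. A reader might also infer that the exposure-response work is affected, but 11.5 uses Cmax or AUC0-t. CL/F and Vz/F are already limited to Day 1.

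**The size is assumed and partly capped.** This stands. With a half-life of 1 h or less the excess is negligible, and the residual-area rule keeps larger cases out of the summaries.

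**The replacement carries a larger error than the one it removes.** This does not stand. The error over the 2 to 8 h gap is just as large in the plan's AUC0-inf, and the interval AUC is never the worse of the two.

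**Using the pre-dose trough as the 12 h value is unsafe.** This stands. 11.3.1 and 11.4 rule out estimates for missing samples and further imputation. If the second dose follows the 8 h sample, the next morning's trough falls about 16 h after the previous dose. In a one-compartment decline it would then be e^(−4k) of the 12 h value: 25% at a 2 h half-life and 45% at 3.445 h.

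**Conclusion.** The point holds as a minor defect of the PK section. Without any half-life assumption, a listed endpoint has no derivation and no summary row, and neither Day 7 AUC is defined over the 12 h interval that 4.5 implies.

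The size of the AUC0-inf excess rests on an assumed half-life, log-linear decline and tau = 12 h: from about 0% at 1 h or less, through 1.6% at 2 h and 6.7% at 3 h, to about 10% at the edge of the residual-area rule. Beyond that edge, larger excesses appear only as flagged listing values. The consequence is confined to descriptive tables and listings for a subset with about 20 active patients, fewer on Day 7 because discharged patients are not sampled. The efficacy analyses are untouched.

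**What to change.** 1. Reconcile the label of the 8 h sample in 11.1 with the dosing interval in 4.5, and state the tau used in the calculation.
2. In 11.2, for Day 7, replace AUC0-inf and residual area with AUCtau = AUC0-t to 8 h plus the part from 8 h to tau obtained from Kel. Report it only where Kel meets the criteria already in 11.2.
3. Define average steady-state concentration = AUCtau/tau.
4. Add both to the table in 11.4.1. Keep AUC0-inf and residual area for Day 1 only.
5. Do not use the pre-dose trough as a 12 h value.

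The cost is a few lines in 11.2, additions to 11.4.1 and the reconciliation in step 1; no new samples are needed. Two limits remain. Patients without an estimable Kel will have no interval AUC, as already happens with AUC0-inf: 11.2 needs three points after Cmax, and a Cmax at 60 min or later leaves at most two within 8 h. The linear-trapezoid error over the 2 to 8 h gap also stays.

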11.3. Presentation of Concentration Data

11.3.1. Handling of Missing Data

Missing concentration data for all patients who are administered study drug will be considered as noninformative missing and will not be imputed. No concentration estimates will be provided for missing sample values.

11.3.2. Handling of the Difference between the Scheduled (nominal time) and the Actual Sampling Times (actual time)

For all sampling times, the actual sampling times relative to dosing are calculated as the difference between the actual clock time of sampling and the actual clock time of dosing. The actual post-dose sampling times relative to dosing expressed in hours and rounded off to three decimal digits are used, except for pre-dose samples occurring prior to dosing, which are reported as zero (0.000), regardless of the time difference. Scheduled sampling times are presented in concentration tables. If the actual time of sampling is missing, the nominal time is used.

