11.4. PK Parameters Derivation

For the derivation of PK, the following rules will apply:

- All plasma concentrations BLQ will be imputed with a value of zero;
- The sampling time of pre-dose samples relative to dosing will also be treated as zero;
- Actual blood sampling times will be used to derive PK parameters. If the actual blood sampling is
 not present, then that time point will not be considered for PK analyses.

This document is confidential.

SAP Text Version: 2.0, 31-Aug-2022 Controlled Document ID: CC , Effective Date 31-Aug-2020 Filing requirements: TMF

Page 41 of 56

- If the pre-dose sample is not present, then that patient will not be considered for PK derivation;
- No further imputation will be applied to any missing values.

All PK parameters will be listed.

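### One missing pre-dose sample removes a patient from all PK derivation, and the linear AUC rule can overstate AUC0-t across the unsampled 2-8 h decline if the half-life is short

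*SAP*

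**What the plan says.** Three rules in SAP section 11 matter here.

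- **Pre-dose rule.** Section 11.4: "If the pre-dose sample is not present, then that patient will not be considered for PK derivation". It acts on the patient, and does not separate Day 1 from Day 7 or one parameter from another.
- **AUC rule.** Section 11.2 defines AUC0-t as "Area under the concentration-time curve from time zero to the last non-zero concentration", and its calculation "will be done using the linear trapezoidal method using linear trapezoidal linear interpolation". The non-compartmental parameters are derived "using up to 8 hours post-dose, on Day 1 and Day 7". Section 11.1 places the later samples at "60 minutes, 120 minutes, 8 hours (before next dose), and 24 hours before the next morning dose", so nothing is drawn between 2 h and 8 h.
- **Missing times.** Section 11.3.2: "If the actual time of sampling is missing, the nominal time is used". Section 11.4 says that if the actual blood sampling is "not present, then that time point will not be considered for PK analyses".

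Other rules bear on the result. Values below the limit of quantification (BLQ) are set to zero. Kel needs at least 3 points after Cmax. AUC0-inf, CL/F and Vz/F leave the summaries when the residual area exceeds 20%. CL/F and Vz/F are Day 1 only. Missing concentrations are not imputed (sections 11.3.1 and 11.4).

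**The concern.** PK of MP1032 on Day 1 and Day 7 is a secondary objective (SAP section 3.2), resting on about 20 active patients. Two features work against it.

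First, the pre-dose rule can discard a usable profile, or a patient's two profiles, over a single sample. For Day 1 that sample's value is already known, because the patient has had no MP1032.

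Second, a straight line between two points on an exponentially falling curve lies above the curve. With one 6-hour trapezoid over the decline, the 2-8 h area can only be overstated when both ends are quantifiable. The excess passes into AUC0-inf, residual area, CL/F and Vz/F where these are reported, and into the optional exposure-biomarker scatterplots, which may use AUC0-t.

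The two statements on missing times add a smaller problem: it is unclear whether a sample with a known concentration but no recorded time is used at its nominal time or dropped.

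**Working it through.** **Schedule.** 8 time points × 2 days = 16 samples; 16 × 4.9 mL = 78.4 mL. Both match section 11.1. The SAP gives no half-life, quantification limit or size of AUC error, so there is no further figure to reproduce.

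**Pre-dose exclusion.** 1/20 = 5% of the active PK patients per exclusion. The SAP gives no rate of missing pre-dose samples, so this is a cost per event and not a forecast.

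**AUC, the 2-8 h segment alone.** For mono-exponential decline with rate k = ln 2 / half-life and r = exp(−6k), the linear area over the true area is [6(1 + r)/2] / [(1 − r)/k].

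- Half-life 1 h: r = 0.0156; 3.047 / 1.420 = 2.15 (+114%)
- 2 h: r = 0.125; 3.375 / 2.525 = 1.34 (+34%)
- 3 h: r = 0.25; 3.750 / 3.246 = 1.16 (+16%)
- 4 h: r = 0.354; 4.061 / 3.731 = 1.09 (+9%)
- 6 h: r = 0.5; 4.500 / 4.328 = 1.04 (+4%)

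**AUC, the whole 0-8 h window.** Assumptions: single dose, one compartment, first-order absorption with ka = 3 or 6 per hour, C(t) proportional to ka/(ka − k) × [exp(−kt) − exp(−ka·t)]. The curve is read at 0, 10, 20, 30, 60 and 120 min and 8 h, and the 8 h value is taken as quantifiable. Each cell gives ka = 3, then ka = 6.

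| Half-life | Linear AUC0-8 vs true | Linear-up/log-down vs true | Points after Cmax | Residual area (linear) | CL/F error (linear) |
|---|---|---|---|---|---|
| 1 h | +35%, +32% | −1.9%, −1.4% | 3, 4 | 0.4%, 0.3% | −26%, −24% |
| 2 h | +17%, +16% | −1.1%, −0.7% | 2, 3 | 6%, 6% | not reported, −13% |
| 3 h | +9%, +9% | −0.9%, −0.5% | 2, 3 | 16%, 15% | not reported, −7% |
| 4 h | +5%, +5% | −0.7%, −0.4% | 2, 3 | 26%, 25% | not reported, excluded |
| 6 h | +2%, +2% | −0.6%, −0.4% | 2, 3 | 41%, 40% | not reported, excluded |

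At 8 h and 12 h the linear excess is about 1% and under 0.5%.

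The last column applies the SAP's own filters. With ka = 3 and a half-life of 2 h or more, the observed peak is at 60 min. That leaves only the 2 h and 8 h points, so Kel and everything built on it is not reported. With ka = 6 and 4 h or more, the residual area exceeds 20%, so CL/F leaves the summaries. Of the eight scenarios from 1 to 4 h, four give a summarised CL/F, and in those it is low by about 7% to 26%.

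**If the 8 h sample is BLQ.** At a 1 h half-life the modelled 8 h level is 0.6-0.8% of Cmax. If it is BLQ it becomes zero, AUC0-t stops at 2 h, and the linear result is 28% (ka = 6) to 33% (ka = 3) below the true AUC0-8. Log-down gives 29% to 34% below, so it does not help there.

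**Missing times.** Section 11.3.2 keeps the time point at its nominal time. The section 11.4 sentence follows one about actual sampling times, yet its subject is the sampling, not the time. Read as a missing time, it contradicts section 11.3.2. Read as a missing sample, it does not, and nothing recoverable is lost.

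**The case against.** The linear trapezoid is a recognised, pre-specified non-compartmental method, the subset is described as sparsely sampled, and the PK output is descriptive. That stands, so log-down is an improvement and not the correction of an error.

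A reader might infer that the plan's AUC is biased upward, with CL/F and Vz/F too low throughout. The SAP does not support that. The size depends on a half-life it never states, the excess is about 2% or less from 6 h, a BLQ 8 h sample reverses the sign, and the Kel and residual-area rules remove CL/F in half of the 1-4 h scenarios. The largest overstatement, at 1 h, is also the case where the 8 h sample is most likely to be BLQ.

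A reader might also infer that sections 11.3.2 and 11.4 certainly give different AUCs from the same data. They do so only on one of two readings. Section 11.3.2 also sits under the presentation of concentrations, while section 11.4 governs derivation.

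The exposure-biomarker work is optional and may use Cmax, which the AUC rule does not touch. A proportional error common to all patients would leave both correlation coefficients unchanged.

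None of this answers the pre-dose rule, which is broader than its purpose needs. A missing Day 7 pre-dose value does affect that day's AUC and Ctrough, but nothing else.

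**Conclusion.** The pre-dose exclusion is unnecessarily wide whatever the half-life, at about 5% of the active PK patients each time it is triggered.

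The AUC point is conditional. With a quantifiable 8 h sample and a half-life of about 4 h or less, AUC0-t is overstated by roughly 5% to 35%, and any CL/F that survives the SAP's filters is understated by about 7% to 26%. These figures rest on an assumed single-dose, one-compartment oral model with ka of 3 to 6 per hour. They are a range and not an estimate for MP1032.

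The missing-time wording is ambiguous and needs reconciling; a definite contradiction is not established.

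The effect is confined to descriptive PK summaries and listings. The efficacy conclusions are untouched. The change is worth making because it is cheap and settles which patients and which AUC values are reported for a stated objective.

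**What to change.** 1. **Section 11.4, Day 1.** Set a missing Day 1 pre-dose concentration to zero, written as an explicit exception to the no-imputation rules in sections 11.3.1 and 11.4.
2. **Section 11.4, Day 7.** If the Day 7 pre-dose sample is missing, exclude only the Day 7 parameters that need it (AUC, Ctrough). Keep Day 7 Cmax and tmax and the whole Day 1 profile.
3. **Section 11.2.** Use linear-up/log-down for AUC. Flag profiles whose 8 h sample is BLQ, since this change does not recover their missing area.
4. **Sections 11.3.2 and 11.4.** Separate the two cases in both places: actual time missing (nominal time used, flagged) and sample missing (time point omitted).

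The cost is SAP wording and one software setting, with no extra samples. The downside is that AUCs become less directly comparable with any earlier linear-trapezoid results; listing the linear AUC as a sensitivity value covers that.

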11.3. Presentation of Concentration Data

11.3.1. Handling of Missing Data

Missing concentration data for all patients who are administered study drug will be considered as noninformative missing and will not be imputed. No concentration estimates will be provided for missing sample values.

11.3.2. Handling of the Difference between the Scheduled (nominal time) and the Actual Sampling Times (actual time)

For all sampling times, the actual sampling times relative to dosing are calculated as the difference between the actual clock time of sampling and the actual clock time of dosing. The actual post-dose sampling times relative to dosing expressed in hours and rounded off to three decimal digits are used, except for pre-dose samples occurring prior to dosing, which are reported as zero (0.000), regardless of the time difference. Scheduled sampling times are presented in concentration tables. If the actual time of sampling is missing, the nominal time is used.

11.3.3. Listing and Presentation of Individual PK Data

- The sampling time of pre-dose samples relative to dosing is treated as zero for all sampling periods separately;
- · All concentrations are presented in original units as reported by Bioanalytical lab, eg, ng/mL;
- All concentrations that are below the lower limit of quantification (BLQ) will be set to zero;

This document is confidential.

Page 40 of 56

- Listing of PK sampling times including nominal and actual time elapsed from dose with the deviation from the nominal time and measured concentrations of the drug;
- · No further imputation will be applied to any missing values.

Individual PK concentration data will be listed by patient ID, time point and treatment (in relevant concentration units).

The individual plasma concentrations for MP1032 will be presented graphically on both the linear and semi-logarithmic scales of Day 1, and Day 7 separately.

